### Missing data

The questionnaires will be web-based and every question will, if technically possible, be mandatory. However, should there for some reason be missing values, they will be replaced with the value corresponding to "no change", i.e. a missing value at follow-up will be replaced with the participant's baseline value and a missing value at baseline will be replaced with the follow-up value. A missing answer in the PGI-I at follow-up will be assumed as "unchanged".

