## Procedure

Participants are consecutively recruited through our website [tät.nu](http://tät.nu). They answer an online screening survey with automated immediate response for initial screening of eligibility criteria. Informed consent and leakage diary (number of episodes of urinary leakage during 48 hours) are sent by post. After that, they answer a web questionnaire and finally they are interviewed by a researcher to confirm the diagnosis UUI or MUUI, to discover any alarm symptoms motivating directing the participant to other care, and to ascertain that the patient is well informed of the study procedure. Women are then randomized to either of the two groups. Women in both groups get a smartphone application for iPhone or Android. The treatment app group receives a unique code for activation of the complete app. Follow-up after three months with a web questionnaire and a leakage diary. After that the information app group get their unique activation code.

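### The SAP fills a missing baseline with the follow-up value, which is measured after randomisation; this forces the change for that value to zero and discards a valid follow-up

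*Combined protocol and SAP*

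**What the plan says.** The SAP's Missing data section applies a no-change rule in both directions. For follow-up, "a missing value at follow-up will be replaced with the participant's baseline value". For baseline, "a missing value at baseline will be replaced with the follow-up value". The safeguard offered is that the questionnaires are web-based and "every question will, if technically possible, be mandatory".

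The protocol's Procedure section gives the order of events. The mailing to women who pass the online screening is described first: "Informed consent and leakage diary (number of episodes of urinary leakage during 48 hours) are sent by post". The questionnaire and the interview are the next two steps: "After that, they answer a web questionnaire and finally they are interviewed by a researcher". Allocation is placed behind all of these: "Women are then randomized to either of the two groups". Later comes "Follow-up after three months with a web questionnaire and a leakage diary". The baseline steps therefore come before allocation, but the section does not say that a returned diary and a complete questionnaire are conditions of being randomised.

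The Primary outcome section of the SAP defines the endpoint as the between-group difference in mean ICIQ-UI SF change, analysed with a linear mixed model.

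**The concern.** A baseline is useful because treatment cannot have affected it. A baseline copied from follow-up does not have that property: in the treatment app group it is a value recorded after the woman has had the app. The change becomes follow-up minus follow-up, which is zero, even for a woman who answered everything at follow-up and improved.

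This differs from the other half of the rule. Filling a missing follow-up from baseline at least uses a pre-randomisation value, and it deals with drop-out that cannot be wholly prevented. A missing baseline can be prevented, because each woman is interviewed before she is allocated.

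At stake are the size of the estimated treatment effect, the within-group tests of change, which are also pulled towards zero, and some power. The rule also yields no value when both time points are missing.

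**Working it through.** **Inputs from the protocol's Sample size section:** mean improvement of 2.5 points (treatment app) and 0.9 (information app); two-sided 5% test; 80% power; 49 per group, raised to about 60 for 20% drop-out. The difference is 2.5 − 0.9 = 1.6.

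**Assumption:** a share m of women in an arm lacks a baseline ICIQ-UI SF score, unrelated to her outcome. The documents give no rate, so m = 2%, 5% and 10% are illustrations.

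**Step 1, the plan's own figure.** No SD is stated, so 49 cannot be reproduced directly. Solving backwards for 49 per group, difference 1.6 and 80% power gives an SD of change of 2.80 (t-test) or 2.83 (normal approximation). For drop-out, 49 / 0.8 = 61.25 and 49 × 1.2 = 58.8, both consistent with about 60. I use 2.80 below.

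**Step 2, the estimate with equal missingness in both arms.** Each filled woman contributes zero, so the expected difference is (1 − m) × 2.5 − (1 − m) × 0.9 = 1.6 × (1 − m):

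- m = 2%: 1.6 × 0.98 = 1.57
- m = 5%: 1.6 × 0.95 = 1.52
- m = 10%: 1.6 × 0.90 = 1.44

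**Step 3, the estimate with missingness in one arm only (10%).**

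- Treatment app arm only: 2.5 × 0.9 − 0.9 = 1.35
- Information app arm only: 2.5 − 0.9 × 0.9 = 1.69

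The second lies further from zero than the true 1.6.

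**Step 4, power.** The zeros reduce the variance as well as the mean, so the SD should not be held at 2.80. In an arm with mean change μ the variance becomes (1 − m) × SD² + m × (1 − m) × μ². At m = 10%, with SD² = 7.83:

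- Treatment app: 0.9 × 7.83 + 0.09 × 6.25 = 7.61
- Information app: 0.9 × 7.83 + 0.09 × 0.81 = 7.12
- Standard error at 49 per group: √((7.61 + 7.12) / 49) = 0.548
- Ratio: 1.44 / 0.548 = 2.63, which gives power of about 74%

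Holding the SD fixed would give 71%, which overstates the loss. The comparison column below drops the affected women, so the difference stays at 1.6 with 49 × (1 − m) per group.

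| m | Expected difference | Power with fill, 49 per group | Power if the women are lost, 49 per group | Power with fill, 60 per group, no follow-up loss |
|---|---|---|---|---|
| 0 | 1.60 | 80% | 80% | 87% |
| 2% | 1.57 | 79% | 79% | 86% |
| 5% | 1.52 | 77% | 78% | 85% |
| 10% | 1.44 | 74% | 76% | 82% |

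At 10% and 49 per group, about 4 of the 6 points lost would go even if the women were just excluded. The fill itself costs about 2 points there and about 1 point at 5%.

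**Step 5, item or score.** Steps 2 to 4 treat the whole score as missing. The Outcome Measures section lists three items in the ICIQ-UI SF. If one item is missing and only that item is filled, only its part of the change is zeroed, and the effect is smaller than shown.

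**The case against.** The strongest reply is that this will hardly ever happen for the primary outcome. The ICIQ-UI SF is completed on the web before randomisation, with items meant to be mandatory. At 2% missing the estimate moves by 0.03 points and power by about 1 point. The follow-up half of the rule, facing the plan's own 20% expected drop-out, matters more. Intention-to-treat with filling would also analyse about 60 per group rather than 49, though follow-up fills would lower the power shown for 60. All of this stands, and it limits the size of the point. It does not make the rule sound: the SAP prespecifies a treatment of missing baselines that gives a wrong value whenever it is used.

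Four stronger readings are tempting, but the documents do not support them.

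- **That the SAP expects women to be randomised without a baseline.** The Missing data section words the rule as a contingency, and it fits a single unanswered item equally well. The Procedure section suggests a complete baseline by its ordering, without requiring it.
- **That the rule certainly covers the IEF baseline.** That value comes from a posted diary, which mandatory web fields do not protect, so a gap is more plausible there. But the section opens with web questionnaires, and its reach to the diary is an inference.
- **That filled values enter the baseline comparison of the groups.** Neither section says whether that comparison uses filled data.
- **That the bias always runs towards zero.** That needs similar missingness in the two arms, as step 3 shows.

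**Conclusion.** The point holds. The clause puts a post-randomisation measurement in the place of a baseline, sets the change for that value to zero and throws away a valid follow-up. With equal missingness the expected ICIQ-UI SF difference falls in proportion to m, to between 1.57 and 1.44 for m from 2% to 10%. With 10% missing in one arm only it could be 1.35 or 1.69. These figures rest on the plan's assumed changes, on wholly missing scores and on assumed rates. The power figures also rest on an SD inferred from the sample size.

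A reader might infer that the primary result is in serious danger. The documents do not support that: the web safeguard should keep m low, and most of the power loss comes from lacking the baseline rather than from the fill. The case for change is the validity of the estimate and the ease of prevention, with IEF the likelier place for trouble if the rule is applied to the diary.

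**What to change.** 1. **Protocol, Procedure.** Add that a woman is randomised only once her leakage diary and a complete baseline questionnaire have been received, with any gap closed no later than the interview.
2. **SAP, Missing data.** Delete the clause that fills a missing baseline from follow-up, and say whether a value means an item or a score.
3. **Residual gaps in ICIQ-UI SF, ICIQ-LUTSqol, ICIQ-OAB or ICS.** Fit the planned linear mixed model to the observed values without filling the baseline. For this to retain women who have only a follow-up value, baseline must enter as one of the repeated outcome measurements; as a covariate it would exclude them.
4. **Residual gaps in IEF or incontinence aids.** Analyse women with an observed baseline. Filling with a pooled mean would suit these rank-based comparisons poorly, and the mixed model makes it unnecessary for the scores.
5. **No-change fill of baseline.** Keep it at most as a sensitivity analysis.

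The cost is a sentence in the protocol and a short edit to the SAP. In practice a few women will have to be chased, or will not be randomised until their baseline is complete; the interview already provides the contact. The follow-up half of the rule is a separate matter that these changes leave in place.

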## Outcome Measures

### 1. Primary Outcome Measure

Measure Title	International Consultation on Incontinence Modular Questionnaire Urinary Incontinence Short Form (ICIQ-UI SF)
Measure Description	Three items on frequency, amount of leakage and overall impact. Scoring 0-21, higher values indicating increasing severity

### 2. Secondary Outcome Measure:

Measure Title	International Consultation on Incontinence Modular Questionnaire Lower Urinary Tract Symptoms Quality of Life (ICIQ-LUTSqol)
Measure Description	The instrument includes 19 items on the impact of the leakage. All items are scored 1-4 (not at all/never, slightly/sometimes, moderately/often, a lot/all the time). The overall score is 19-76, with higher values indicating increased impact on QOL.

### 3. Secondary Outcome Measure:

Measure Title	International Consultation on Incontinence Modular Questionnaire Overactive Bladder (ICIQ OAB)
Measure Description	Four items on frequency of micturition during day and during night, frequency of urgency and urgency leakage, each item scored 0-4, total score 0-16, higher values indicating increased severity.

### 4. Secondary Outcome Measure:

Measure Title	Incontinence catastrophizing scale (ICS)
Measure Description	Seven items on fear of leakage and urgency. Alternatives on each item; Never (=0), sometimes (=1), often (=2), Always (=3). Score 0-21.

### 5. Secondary Outcome Measure:

Measure Title	Incontinence Episode Frequency (IEF)
Measure Description	number of incontinence episodes per week

### 6. Secondary Outcome Measure:

Measure Title	Change from baseline Usage of incontinence aids at 15 weeks
Measure Description	Use of incontinence aids during the last four weeks, six response options from "Never" to "more than one incontinence aid per day"

### 7. Secondary Outcome Measure:

Measure Title	Patient global impression of improvement (PGI-I)
Measure Description	Validated 7-item scale on improvement from very much improved to very much worse.

**8. Secondary Outcome Measure** (only for the Tät® II treatment app group):

Measure Title	Patient Satisfaction
Measure Description	A self-rated question about if the current treatment was sufficient, with three response options (satisfied without any leakages remaining; satisfied with leakages remaining; not satisfied)

